The elbow angle is measured using a variable resistor (RV09H-20SQ, 50 k Ω). A goniometer marked in 1-degree increments from 0° to 150° is placed on the inner and outer surfaces of a box, aligned with the flexion and extension directions of the elbow joint. Velcro straps are used to secure the participant's upper limb to the inner goniometer, fixing the elbow joint and the distal radius and ulna in place. As the participant moves their arm, the inner goniometer moves accordingly, allowing the current elbow angle to be measured. A pointer is attached to the outer goniometer to enable the participant to indicate the angle. To ensure that the participant cannot

[figure not shown]
see their moving limb, the inner and outer goniometers are enclosed within a box of suitable size, as illustrated in <Figure 4>.

The resistance value measured via the variable resistor is converted into the corresponding elbow angle. Based on the measured elbow angle, the electrical stimulation frequency is adjusted accordingly for the experiment. The conversion formula for mapping elbow angle to electrical stimulation frequency is as follows:

$$F_{stim} = \frac{(F_{max} - F_{min})}{(\theta_{max} - \theta_{target})} (\theta_{current} - \theta_{target}) + F_{min} \quad \theta_{target} \leq \theta_{current} \leq \theta_{max}$$

$$F_{stim} = \frac{(F_{min} - F_{max})}{(\theta_{target} - \theta_{min})} (\theta_{current} - \theta_{target}) + F_{min} \quad \theta_{min} \leq \theta_{current} \leq \theta_{target}$$

θ_{target} denotes the target angle to be learned, which is set differently depending on the experimental condition. θ_{max} and θ_{min} are defined as $\theta_{target} + 15^\circ$, $\theta_{target} - 15^\circ$, respectively. F_{max} and F_{min} are set to 70 Hz and 10 Hz, respectively. $\theta_{current}$ represents the current elbow angle, and F_{stim} denotes the electrical stimulation frequency corresponding to the current elbow angle.

<Figure 4. Box-Type Elbow Angle Measurement Device>

2) Methods

2-1) Study Period

The total study duration spans a minimum of three weeks. For each of the three experimental conditions, assessments are conducted during Visit 1 and Visit 2, with a washout period of at least 7 days between conditions.

2-2) Randomization and Procedure

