2-4-3) No Cue Protocol

The intervention is administered once for 30 minutes. The participant attempts to match their elbow joint angle to a verbally instructed target angle, relying solely on verbal feedback from the examiner.

2-5) Outcome Measures and Assessment Procedures

2-5-1) Threshold Detection

An angle-detecting sensor developed by the research team (see Section 1-3) is attached to the participant's affected elbow joint. The examiner holds the medial and lateral epicondyles of the participant's affected upper limb with one hand and the distal radius and ulna with the other. The test is conducted four times in total: two trials in the flexion direction and two in the extension direction, in random order. Each trial starts from 60° of elbow flexion. The examiner moves the joint at approximately 6° per second, and the participant is instructed to verbally report when they perceive joint movement. If the participant does not respond before the joint reaches 30° of motion, a score of 0 is recorded.

-2 points: Participant perceives movement of the elbow joint.

-0 points: Participant does not perceive movement of the elbow joint.

2-5-2) Joint Position Reproduction

[figure not shown]
An angle-detecting sensor developed by the research team is attached to both of the participant's elbow joints. The examiner holds the medial and lateral epicondyles of the participant's affected upper limb with one hand and the distal radius and ulna with the other. The examiner passively moves the affected arm to one of 12 pre-defined flexion or extension angles in the following order: 60°, 90°, 30°, 120°, 60°, 30°, 90°, 120°, 30°, 60°, 120°, and 90°. After each presentation, the participant is asked to reproduce the same angle using the unaffected limb. The average difference between the target angles and the reproduced angles across the 12 trials is calculated and used for analysis.

2-5-3) position Sense Test

Apparatus

Goniometers marked in 1-degree increments from 0° to 120° are installed on the inner and outer surfaces of a box aligned with the elbow joint's flexion and extension axis. Velcro straps are used to secure the participant's upper limb and distal radius and ulna in place. A pointer is attached to the outer goniometer to allow the participant to indicate the perceived angle. A box of appropriate size is placed between the inner and outer surfaces to block the participant's view of their own arm during the test.

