* The apparatus was newly designed with reference to the Wrist Position Sense Test Apparatus (see Figures 4 and 6).

<그림 6. Wrist position sense test apparatus>

Procedure

The examiner passively moves the participant's upper limb to one of 12 predefined elbow flexion or extension angles in the following order: 60°, 90°, 30°, 120°, 60°, 30°, 90°, 120°, 30°, 60°, 120°, and 90°. The examiner attempts to maintain a consistent speed during both flexion and extension movements. After the target angle is reached, the participant uses their contralateral (unaffected) hand to indicate the perceived angle by adjusting a pointer on the outer goniometer of the device. The absolute differences between the presented and indicated angles are recorded for each of the 12 trials, and the average error is calculated for analysis.

2-5-4) Motor & Position Sense Test

Apparatus

Goniometers marked in 1-degree increments from 0° to 120° are installed on both the inner and outer surfaces of a box aligned with the flexion and extension axis of the elbow joint. Velcro straps are used to secure the participant's upper limb, including the elbow joint and distal radius and ulna. A pointer is attached to the outer goniometer to allow participants to indicate perceived joint angles. A box of appropriate size is placed between the inner and outer goniometers to ensure that the participant's tested arm remains out of view during the assessment.

Procedure

After assessing the participant's upper limb range of motion (ROM), the examiner manually moves the goniometer pointer to present 12 different target angles within the participant's available ROM. The participant is instructed to actively move their elbow joint to match the presented angle by flexing or extending the joint. During each trial, the participant is encouraged to move at a consistent speed. After the examiner presents the target angle using the pointer, the participant moves their limb to the angle they perceive as matching the target. The difference between the presented and perceived angles is recorded for each of the 12 trials, and the average error is calculated for analysis.

2-5-5) Fugl-Meyer Assessment (FMA): Upper Limb Position Sense Test

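### Section 2-5-3 marks its response scale 0-120° yet presents 120° in 3 of 12 trials, while Section 1-3 gives 0-150° for what appears to be the same box

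*Protocol*

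**What the plan says.** Section 2-5-3, Apparatus: "Goniometers marked in 1-degree increments from 0° to 120° are installed on the inner and outer surfaces of a box". Its Procedure moves the limb through "elbow flexion or extension angles in the following order: 60°, 90°, 30°, 120°, 60°, 30°, 90°, 120°, 30°, 60°, 120°, and 90" degrees. The participant then uses the unaffected hand to "indicate the perceived angle by adjusting a pointer on the outer goniometer of the device". Scoring: "The absolute differences between the presented and indicated angles are recorded for each of the 12 trials", and these are averaged.

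Section 1-3 also describes a box with inner and outer goniometers, Velcro straps and an outer pointer, but with a longer scale: "A goniometer marked in 1-degree increments from 0° to 150° is placed on the inner and outer surfaces of a box". It points to Figure 4: "the inner and outer goniometers are enclosed within a box of suitable size, as illustrated in <Figure 4>". Section 2-5-3 cites that figure for its own apparatus: "The apparatus was newly designed with reference to the Wrist Position Sense Test Apparatus (see Figures 4 and 6".

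Section 2-5-4 repeats the shorter scale: "Goniometers marked in 1-degree increments from 0° to 120° are installed on both the inner and outer surfaces of a box". It presents targets within each participant's range of motion and lists no fixed angles.

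Section 4-5 gives the study's purpose as assessing feasibility and estimating effect sizes for the key outcomes in 10 participants.

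**The concern.** The protocol gives two scale lengths for what looks like one device, and the shorter one ends exactly at the largest angle tested. With absolute error as the score, both directions of error must be readable at every angle. On the 0-120° scale they are not at 120°: a response of 110° scores 10°, while a response meant as 130° has nothing to be read against.

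If overshoots were written down as 120°, they would score as perfect answers. The mean error would then be too small. A participant who improves by ceasing to overshoot would show less gain than one who improves by ceasing to undershoot. A pilot meant to supply effect sizes for later planning should not carry an error of that kind when it can be avoided almost for free. An overshoot that was never read cannot be recovered afterwards.

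**Working it through.** **Inputs from the protocol.** The angle list, marked range, response method and scoring come from 2-5-3; the alternative range comes from 1-3. The protocol gives no bias or SD for the pointing response, so those below are assumptions.

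**Step 1: count the trials.** The list has 12 entries, as the section says: 30°, 60°, 90° and 120°, three times each. The share at 120° is 3/12 = 25%.

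**Step 2: marked scale beyond the extreme angles.**

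| Scale | Below 30° | Above 120° |
|---|---|---|
| 0-120° (2-5-3) | 30 - 0 = 30° | 120 - 120 = 0° |
| 0-150° (1-3) | 30 - 0 = 30° | 150 - 120 = 30° |

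The longer scale leaves equal room at both ends; the shorter leaves none at the top.

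**Step 3: illustration if a setting past 120° is recorded as 120°.** Let e be the signed error. A 120° trial then contributes E[max(-e, 0)] instead of E|e|. For any error symmetric about zero the first is half the second. With equal spread at all angles, the 12-trial mean falls by 0.25 × 0.5 = 12.5%. Simulation with normal errors gives 3.99 → 3.49 at SD 5° and 7.98 → 6.98 at SD 10°, in agreement. On a 0-150° scale the loss at zero bias is at most 0.5% for SD 5-15°.

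**Step 4: does the direction of error matter?** Assume normal errors with SD s = 10° and the same bias b at all angles. Write φ and Φ for the standard normal density and distribution function.

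- E[max(-e, 0)] = sφ(b/s) - bΦ(-b/s)
- E[max(e, 0)] = sφ(b/s) + bΦ(b/s)
- E|e| is the sum of the two.
- Recorded mean = 0.75 E|e| + 0.25 E[max(-e, 0)]

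For b = +5°: E[max(-e, 0)] = 3.52 - 1.54 = 1.98 and E[max(e, 0)] = 3.52 + 3.46 = 6.98, so E|e| = 8.96. The recorded mean is 0.75 × 8.96 + 0.25 × 1.98 = 7.21. For b = -5° the two parts swap: 0.75 × 8.96 + 0.25 × 6.98 = 8.46. For b = 0: 0.875 × 7.98 = 6.98.

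| Bias removed | True improvement | Recorded improvement |
|---|---|---|
| +5° to 0° | 8.96 - 7.98 = 0.98° | 7.21 - 6.98 = 0.23° |
| -5° to 0° | 8.96 - 7.98 = 0.98° | 8.46 - 6.98 = 1.48° |

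Equal true gains are recorded unequally, according to the direction of the starting error. The degrees shown depend wholly on the assumed bias, SD and recording rule.

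**The case against.** The strongest reply is that no ceiling is documented. The protocol gives graduations only. It does not say that the pointer stops at 120°, or that a setting beyond it is entered as 120°. That stands, and every figure in Steps 3 and 4 is conditional on it.

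A second reply is that the two halves of the point pull against each other. If 2-5-3 uses the box described in 1-3 and that description is right, there are 30° of room and only the text is wrong. If the devices differ, there is no contradiction. This also has force. Figure 4 is not shown, so a reader might infer that the two sections are proven to describe one device. The shared figure reference and the matching description make that likely, not certain. On either reading, however, 2-5-3 as written has no marks above its largest angle.

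A third reply is that each participant receives all three conditions with a baseline before each, so a ceiling would affect every condition. That is true, but it cancels only if the bias at 120° stays constant, and the training aims to reduce matching error. It is fair that the effect is small beside the pilot's imprecision. Under the zero-bias illustration, and if trial noise is the only variance, a standardised change falls by about 12%. On an assumed change of 0.5 that is 0.5 × 0.12 = 0.06, against an approximate 95% half-width of 1.96 × √(1/10 + 0.5²/20) = 0.66 with 10 participants.

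The elbow sensor does not settle the matter. The resistor in 1-3 is described as measuring the elbow angle, while the response in 2-5-3 is the outer pointer. Section 2-5-2 does test the same 12 angles with sensors on both elbows, so that measure does not depend on this scale.

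**Conclusion.** The point holds as a minor inconsistency with a possible measurement consequence. Established from the text: two scale lengths for what appears to be one box, and, on the shorter scale, 0° of marks above an angle presented in a quarter of the trials. An overestimate there cannot be read from the scale as described, while an underestimate can.

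Not established: that responses are truncated at 120°, that the outcome is biased in practice, or by how much. A reader might take 12.5% as the expected bias. It is an illustration that assumes symmetric errors with no bias, equal spread at all angles, and overshoots entered as 120°; it describes the level of the mean error and is not an estimate of bias in a comparison between cues. One of eight measures is affected, and 4-5 does not name it as a key outcome. Section 2-5-4 shares the inconsistent description, but it lists no fixed angles and its response is the elbow movement itself, so the same ceiling is not shown there.

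**What to change.** Check the device actually built and make Sections 1-3, 2-5-3 and 2-5-4 agree with it. In 2-5-3, state a response scale that extends beyond the largest presented angle, such as the 0-150° scale already described in 1-3, so that an overshoot at 120° is read and scored like any other error. If the two sections really describe different devices, say so.

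If the device is marked 0-150°, the cost is a correction of wording. If its scale does end at 120°, the outer scale has to be extended before the first assessment, and the angle list can stay as it is.

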All participants enrolled in the study are assigned a random number generated using Python. Based on a pre-defined randomization protocol, each participant is randomly allocated to a specific sequence of the three experimental conditions: Electrical Stimulation Cue, Visual Cue, and No Cue.

2-3) Visit Schedule

All participants receive standard therapy in accordance with clinical guidelines for stroke rehabilitation. The study intervention is provided in addition to standard therapy. A total of six visits are planned. During the screening visit, participants (or their legal representatives) provide written informed consent. The participant's medical history and current clinical status are reviewed to confirm eligibility. Eligible participants are then assigned a randomization number and allocated to a randomized order of the three cueing conditions: Electrical Stimulation Cue, Visual Cue, and No Cue.

Baseline assessments are conducted at Visit 1, Visit 3, and Visit 5—prior to the start of each intervention. After the baseline assessment, one session of the corresponding intervention is administered. Following each intervention session, additional efficacy assessments are performed during all visits. A washout period of at least 7 days is maintained between each experimental condition.

The overall study flow is summarized in Figure 5.

<Figure 5. Study Protocol Flowchart>

2-4) Experimental Intervention Protocols

2-4-1) Electrical Stimulation Cue Protocol

The intervention is administered once for 30 minutes. An electrical stimulation device developed by the research team is attached to the participant's cubital fossa. Stimulation is provided with increasing frequency, reaching a maximum of 70 Hz as the elbow joint approaches a pre-defined target angle. This target angle is individually set within the participant's available range of motion based on baseline assessments. During the session, the participant attempts to match their elbow angle to the target angle while receiving verbal feedback from the examiner.

2-4-2) Visual Cue Protocol

The intervention is administered once for 30 minutes. A visual cue displays the difference between the current elbow joint angle and a predefined target angle on a screen. The target angle is individually set within each participant's range of motion based on baseline assessments. The participant is instructed to match their elbow angle to the target angle while receiving verbal feedback from the examiner.

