7-3-3-6) [18] (Korea): Investigated the effects of EMS frequency on performance in a visual stimulus-response task.

7-3-3-7) [19] (Korea): Designed and evaluated a dry e-tactile electrode EMS brace for elite badminton players with knee pain.

7-3-3-8) [20] (Korea): Developed injury-prevention socks integrating EMS and stretch sensors for

home training.

7-3-3-9) [21] (Japan): Studied the early application of EMS to prevent muscle atrophy and weakness after ACL reconstruction.

7-3-3-10) [22] (Japan): Developed a gravity-free training method combining voluntary muscle contractions with electrical stimulation.

7-3-3-11) [23] (China): Created an electric muscle simulator based on functional electrical stimulation (FES).

7-3-3-12) [24] (China): Applied electrical stimulation therapy to treat peripheral nerve injuries.

7-3-3-13) Studies [18], [19], and [20] were conducted on Korean participants.

7-3-3-14) Studies [21] and [22] were conducted on Japanese participants.

7-3-3-15) Studies [23] and [24] were conducted on Chinese participants.

7-3-4) Commercial Personal Electrical Stimulators

The electrical stimulator used in this study operates with lower current and frequency levels compared to specifications of commonly available commercial personal electrical stimulation devices:

-The EMS 1000 (Hyundai Bio Medical Co., Ltd., Seoul, Republic of Korea) specifies a maximum output current of 17 mA and a maximum frequency of 200 Hz.

-The EMGFES 1000 (Cybermedic Co., Ltd., Gwangju, Republic of Korea) specifies a maximum output current of 99 mA and a maximum frequency of 200 Hz.

-The KD-PRO-5000 Gold (Kukdong Electronics Co., Ltd., Incheon, Republic of Korea) specifies a maximum output current of 12.2 mA and a maximum frequency of 1,190 Hz.

-The SERA (GOS Co., Ltd., Gyeongsan, Republic of Korea), a personal rehabilitation walking assist device, specifies a maximum output current of 80 mA and a maximum frequency of 120 Hz.

8) Subject Withdrawal Criteria

8-1) Subjects who exhibit visually identifiable allergic skin reactions upon attachment of the gel-type electrodes, or who report discomfort greater than or equal to 3 on a Likert scale, will be excluded from the study.

8-2) Subjects who consistently report discomfort due to electrical stimulation will also be excluded.

First, stimulation intensity is set significantly lower than the discomfort-inducing threshold to prevent such issues.

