Second, if a subject verbally reports discomfort during the experiment, the procedure will be immediately paused.

After a rest period of approximately 3–5 minutes, the experiment may be resumed.

If discomfort persists upon resumption, the subject will be withdrawn from the study.

9) Research Timeline

Subject recruitment and experimental procedures are scheduled to begin after July 1, 2025.

The study aims to complete experiments with 10 participants by August 31, 2027.

10) Participant Compensation

The electrical stimulation used in this study does not involve invasive therapy; therefore, no known or anticipated adverse effects are expected. However, participants may experience minor discomfort such as skin irritation or slight muscle contractions. In the event of any unexpected incidents during the experiment, the research staff will immediately notify the principal investigator, [name]. If a clear causal relationship is established between the study and any injury, [name] will assume responsibility for compensation and treatment costs.

11) Informed Consent and Study Information Sheet

Please refer to the separately attached document titled "5. Informed Consent Form."

12) Other Ethical Considerations for Research Conduct

All experimenters will thoroughly familiarize themselves with and strictly adhere to this protocol to ensure the ethical conduct of the research. The principal investigator, [name], will periodically assess whether the experimenters fully understand and comply with the protocol.

Expected Outcomes of the Study

Although sensory errors frequently occur after stroke, conventional motor rehabilitation relies mainly on repetitive training without addressing these sensory deficits, resulting in limited effectiveness. This study aims to improve the effectiveness of upper limb and finger motor rehabilitation by delivering proprioceptive information through tactile channels via electrical stimulation (proprioceptive error correction technology). By addressing sensory errors overlooked in traditional rehabilitation, this approach is expected to reduce patients' frustration and fatigue during rehabilitation, thereby significantly enhancing their quality of life despite the time and effort required.

References

- [1] Van Den Berg, A. A. "Skin sensitivity of the arm: A comparison of five sites." *Anaesthesia* 51.2 (1996): 194-197.

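### Sections 8-1 and 8-2 take a participant out of the whole study for a reaction to the stimulation electrodes, so comparator sessions that use no stimulation are lost

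*Protocol*

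**What the plan says.** **Design.** Under Protocol section 2-2, "each participant is randomly allocated to a specific sequence of the three experimental conditions". Section 2-1 assigns two visits to each condition, "with a washout period of at least 7 days between conditions", and section 2-3 plans six visits in all, with one intervention session following the baseline assessment at Visits 1, 3 and 5.

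**Where electrodes are used.** In section 2-4-1, "An electrical stimulation device developed by the research team is attached to the" inside of the elbow. The other two conditions do not mention the device. In 2-4-2, "A visual cue displays the difference between the current elbow joint angle and a predefined target angle on a screen"; in 2-4-3 the participant has only the examiner's spoken feedback.

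**Withdrawal.** Section 8-1 covers people who show a visible allergic skin reaction to the gel electrodes, "or who report discomfort greater than or equal to 3 on a Likert scale, will be excluded from the study". Section 8-2 adds: "Subjects who consistently report discomfort due to electrical stimulation will also be excluded". After a pause of a few minutes "the experiment may be resumed", but "If discomfort persists upon resumption, the subject will be withdrawn from the study".

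**Purpose.** Section 4-5 describes a pilot of 10 people that is to test feasibility and supply effect sizes for planning later studies.

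**The concern.** The rule is wider than the hazard it answers. A skin reaction to gel electrodes, or discomfort from the current, is a reason to stop stimulation. It is not in itself a reason to cancel sessions in which no current is applied. The wording does not look like a slip for ending the session, because 8-2 distinguishes a session that is paused and resumed from removal from the study. Section 4-1 also already contains the narrower action of stopping stimulation when discomfort is reported.

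The within-person comparison is at stake. Visual Cue and No Cue data go missing because of how the person responded to the third condition. An analysis plan may model such gaps, but it cannot restore sessions that were never held. With 10 people, each incomplete set of three conditions counts.

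**Working it through.** The plan states no figure to reproduce on this point. The check is a count from the design, followed by an illustration under assumptions.

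**Inputs.** Three conditions: E (stimulation), V (Visual Cue), N (No Cue), from 2-2. Two visits per condition and six in total, from 2-1 and 2-3. Ten participants, from 4-5. Not given: the set of orders used, when electrode placement and the setting of the voltage range (sections 1-1 and 1-2) take place, the withdrawal rate, and any replacement rule.

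**Case A: the trigger occurs at the stimulation session (Visit 1, 3 or 5).** Conditions after E are lost.

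| Order | Comparator conditions lost | Comparator visits lost (of 4) | V and N both held? |
|---|---|---|---|
| E-V-N | 2 | 4 | no |
| E-N-V | 2 | 4 | no |
| V-E-N | 1 (N) | 2 | no |
| N-E-V | 1 (V) | 2 | no |
| V-N-E | 0 | 0 | yes |
| N-V-E | 0 | 0 | yes |

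If the six orders are equally likely (assumption), the mean loss is (2 + 2 + 1 + 1 + 0 + 0)/6 = 1 of 2 comparator conditions. In 4 of 6 orders the person gives no Visual-versus-No-Cue pair. When E comes first, any stimulation data collected have no within-person comparator. All lost comparator sessions lie in periods 2 and 3.

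**Case B: the trigger occurs at a calibration before period 1.** Both comparator conditions are lost in all six orders, so the loss is 2 of 2 and does not depend on the order.

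**Illustration of precision for the Visual-versus-No-Cue comparison.** Let w of 10 be withdrawn, without replacement and with unchanged spread. The values of w are assumed; the protocol supports none of them.

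- Case A, expected pairs left: 10 − w × 4/6. For w = 1, 2, 3 this gives 9.33, 8.67, 8.00. The standard error ratio √(10/n) is 1.035, 1.074, 1.118, a rise of about 4%, 7% and 12%.
- Case B, or Case A with stimulation never third among those withdrawn: n = 10 − w = 9, 8, 7. The ratio is 1.054, 1.118, 1.195, a rise of about 5%, 12% and 20%.

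**With the rule limited to stimulation.** No comparator condition is lost under this rule in any order in either case. After a stimulation session at Visit 1, 3 or 5, the remaining 5, 3 or 1 planned visits are kept.

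**The case against.** The best defence is that full withdrawal is a cautious choice for a device built by the research team, used in stroke patients who may be cognitively impaired (a K-MMSE score of 10 is eligible under 3-2). Stimulation is also kept below each person's discomfort threshold, raised in 0.1 V steps and limited to 30 V and 10 mA, so withdrawals may be rare. The caution is reasonable, but it is satisfied by stopping stimulation permanently while the investigator keeps the power to end participation. Rarity limits the size of the problem, not its direction.

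Several objections do limit what can be claimed:

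- **Order.** A reader might infer that the loss always depends on the random order. That holds only for triggers in the stimulation period. The protocol does not date the calibration, and 8-1 acts when electrodes are attached.
- **Bias in the effect size.** A reader might infer that the stimulation effect will be overstated because only those who tolerate it remain. That depends on which participants the analysis uses and on how the withdrawn would have responded. The first may be settled in an analysis plan not shown, and the second is unknown. Nor can the fix supply a full stimulation response from someone who could not complete the session.
- **Shrinking sample.** Section 4-5 calls 10 the initial number and section 9 aims to complete 10 people, so replacement is possible. The precision figures above assume none.
- **The discomfort score.** 8-1 does not tie its score of 3 to stimulation. In section 6, item 3 asks about stimulation, but item 1 also covers the band and general setup. A score of 3 is therefore not always a response to the stimulation condition, and continuing a setup that caused it would be wrong.

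**Conclusion.** The point stands in a limited form. For a gel-electrode skin reaction or persisting stimulation discomfort, section 8 cancels Visual Cue and No Cue sessions that need no stimulation electrodes. The loss is 2, 1 or 0 comparator conditions if the trigger falls in the stimulation period with stimulation first, second or third, and 2 if it falls at a calibration before period 1. These counts follow from the design alone.

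The total effect on the pilot cannot be stated, because no withdrawal rate or replacement rule is given. On the assumed 1 to 3 withdrawals without replacement, the loss of precision is modest. The stronger reason to change the rule is that data on two conditions go missing because of a response to the third, in a study meant to supply effect sizes. The documents do not establish a particular bias, and the safety triggers themselves are not at fault. This is a cheap improvement.

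**What to change.** In 8-1 and 8-2, for electrode skin reactions and for discomfort attributed to the electrodes or the stimulation, replace removal from the study with text to this effect:

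- Stimulation is stopped and not given again to that person.
- Unless the person withdraws or the investigator judges it unsafe, the remaining assessments of the stimulation condition are completed.
- The remaining Visual Cue and No Cue sessions are held in the assigned order, after the planned washout and once the skin has settled.

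Keep the existing rule for discomfort of 3 or more attributed to the straps, band or measuring setup, since that setup is used in all conditions. This requires the reason for the discomfort to be recorded with the score. All safety triggers in 7-1, 8-1 and 8-2 stay unchanged; it would help to confirm that ending the experiment in 7-1 means ending the session, which is the sense the word has in 8-2.

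The cost is a few sentences. No procedure or visit is added. The downside is a possible delay, because the straps and angle sensors go on the same arm; the washout is a minimum, so it leaves room for this.
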